Cognitive Recovery With Cannabis Abstinence Among
High School-Aged Adolescents

NCT03276221

Document Date: 04/28/2023

Cognitive Recovery with Cannabis Abstinence Among High-school-aged Adolescents

Statistical Analysis Plan

The ARCHES Team

NCT: 03276221

First created 2/12/2022

Last revised 04/28/2023

Unblinded analysis 02/03/2023

Version 2.2

Table of Contents

Study Design	4
Participants	4
Order of data collection and creation of the analysis plan	5
Analyst-blind	5
Primary Outcomes.....	7
CANTAB tasks	7
Selection of outcomes.....	10
Statistical model.....	15
Key confirmatory effect.....	16
Multiple comparisons.....	16
Covariates	16
Missing data	17
Clinical Significance	17
Secondary analyses	18
Secondary Outcomes	20
CANTAB tasks	20
Selection of outcomes.....	20
Statistical model.....	21
Power	22
Software	24
References	25

Study Design

The study consisted of a one-month (with a two-month follow-up) longitudinal trial of cannabis abstinence (with data collection from 9/2017 to 12/2022) designed to determine:

1. Whether cognitive performance improves for students abstinent from cannabis use for one month above and beyond any improvement observed for students engaging in continued use.
2. When cognitive performance improves (if improvement during abstinence does occur).
3. Whether cognitive performance in abstinent individuals "returns" to performance levels observed in non-using peers.

Participants

The study planned to recruit 210 adolescents across the following conditions:

1. A control group of non-cannabis users (Non-users; n = 70).
2. Regular users of cannabis (n = 140) randomized to either...
 - a. Contingency management intervention that incentivized 4 weeks of cannabis abstinence (CB-Abst; n = 70).
 - b. Non-contingent monitoring with no abstinence requirement (CB-Mon; n = 70).

All participants completed cognitive assessments, toxicology testing, self-report questionnaires and semi-structured mood and substance use interviews during the 4-week study as well as one 30-day follow-up visit. Abstinence was verified using the statistical model of Schwilke and colleagues (2011). The approach differentiates residual cannabinoid excretion from new cannabis exposure by comparing observed urine metabolite ratios against expected ratios. Observed ratios that exceed a 95% confidence interval indicate new cannabis use.

Order of data collection and creation of the analysis plan

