Continuous outcomes (e.g., latencies and reaction times) were fit using a standard linear regression model. Bounded count outcomes (e.g., number of errors or correct responses) were fit using binomial regression. Specifically, let $y_{(p,t)}$ refer to the outcome value for participant p at time t , where $y_{(p,t)} = \{0, 1, \dots, H\}$ with H referring to the highest possible value. We assumed that $y_{(p,t)}$ was distributed according to a binomial process governed by a latent probability $\theta_{(p,t)}$:

$$y_{(p,t)} \sim \text{Binomial}(\theta_{(p,t)}).$$

The log-odds of this latent probability can then be decomposed into the weighted sum of the predictors of interest.

In contrast to linear regression, which includes a parameter for the residual standard deviation, binomial regression has no additional parameter to handle overdispersion. While failure to account for overdispersion can lead to underestimation of standard errors, as noted before the GEE approach is robust to misspecification of distributional assumptions and corrects for this underestimation, and as such we did not need to implement any additional steps to address overdispersion issues.

Key confirmatory effect

The key confirmatory effect of interest for each outcome will be a dummy-coded contrast between CB-Mon (the referent, coded as 0) and CB-Abst (coded as 1), testing whether a constant effect of abstinence exists, averaged over all time points.

Multiple comparisons

Each module/task from the CANTAB examines a separate cognitive process of interest. We therefore address multiple comparisons issues within each module. As the number of outcomes per module range from 1 to 4, we used a simple Bonferroni correction, dividing the desired error rate of 5% by the number of outcomes per module. Therefore, effects of interest were flagged as statistically significant for $\alpha = 0.05$ (for the SST module), $\alpha = 0.025$ (for the PAL, SSP, OTS, and SWM modules), $\alpha = 0.0167$ (for the VRM module), and $\alpha = 0.0125$ (for the MTT module).

Covariates

The covariates we included for the primary analysis were:

- A coefficient for a linear trend to capture change over time, coded as week 1 = -3, week 2 = -1, week 3 = 1, and week 4 = 3.
- A subject's baseline value for a given outcome, converted to a z-score.

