In other words, we assume a conservative additive model, adjusting for baseline levels and with main effects for a) the impact of abstinence and b) change over time, but no treatment by time interaction.

Additionally, to assess the robustness of our conclusions we will incorporate, at a minimum, the following covariates as part of a secondary analysis:

- Age of participant at baseline (in years).
- Biological sex (male versus female).

Baseline scores from the Cannabis Use Disorder Identification Test - Revised (CUDIT-R; Adamson et al., 2010). The CUDIT-R is an 8-item scale with scores ranging from 0 to 32, where higher scores indicate more problematic cannabis use (a score of 8 or higher indicates hazardous use, while a score at or above 12 indicates a possible use disorder).

Missing data

Missing outcome data (e.g., subjects who did not complete all four visits or did not complete all 7 modules during a visit) will be handled using multiple imputation via chained equations (MICE; see for example Azur, Stuart, Frangakis, & Leaf, 2011). Missing outcome values will be imputed 48 times using linear regression and predictive mean matching. We will then apply the statistical model to each combination of observed and imputed data and will pool the resulting set of 48 model results using Rubin's rule. Subjects must have at least one post-baseline data point to be included in an analysis. Note because we are interested in the effect of abstinence, only data with biochemically-verified abstinence will be included – all data for the visit of and subsequent visits in which abstinence was no longer verified will be excluded for CB-Abst subjects. Covariates for imputing missing values will be:

- Non-missing outcome values at other time points;
- Outcome values at the baseline visit;
- The covariates listed above (age in years, biological sex at birth, baseline scores for CUDIT-R, and duration in years spent using cannabis).

Clinical Significance

In addition to determining whether there is a statistically significant difference between groups, we assessed clinical significance by computing standardized effect sizes for all contrasts of interest per each outcome. Effect sizes were estimated by dividing the estimate (transformed when necessary to be in the original scale of the measure) by the standard

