3. We checked whether our conclusions were robust to the inclusion of covariates, examining the inclusion of age, CUDIT-R scores, and biological sex, all assessed at baseline. All covariates were converted into z-scores.
4. We checked whether our conclusions for our primary analysis were robust to our treatment of missing data (i.e., imputation of missing values). We reran the primary analysis using only observed values (we excluded values that were imputed).

Secondary Outcomes

The 2 secondary outcomes for the study were measures taken from the module in the set included in the study that CANTAB designated for assessing the domain of attention (see <https://www.cambridgecognition.com/cantab/cognitive-tests/attention>). While the MOT module is included in this list, as noted before since it is intended primarily for calibration and training, we excluded it from analyses.

CANTAB tasks

The module for assessment of attention was...

1. The Rapid Visual Information Processing (RVP) module.

Description: Subjects saw a sequence of digits appear one at a time in the center of the screen, at the rate of 100 digits per minute. The goal of the task was to indicate as quickly as possible when a target sequence of digits (e.g., 2-4-6) appeared onscreen. There were 54 3-digit target sequences, and 546 single-digit distractors.

Selection of outcomes

Again, for the RVP module we only analyzed the subset of recommended outcomes per CANTAB's manual (Cambridge Cognition, 2021). However, the CANTAB recommends both a measure of discriminability, A' , using signal detection theory (SDT), along with the proportion of false alarms. Because A' is calculated using the proportion of hits and false alarms, we excluded the proportion of false alarms due to redundancy issues. Therefore, there were a total of 2 recommended outcomes, listed below with a brief description and details on the units of measurement, range, and interpretation.

1. Outcomes to assess change in attention functioning:

- 1.1. A measure of discriminability, A' from the RVP module.

- A transformation of the proportion of hits and false alarms, providing an estimate of a subject's ability to detect the target sequences of digits after controlling for

response bias (i.e., biases to respond or not respond irrespective of the stimuli on screen).

- Bounded continuous variable, ranging from 0 to 1, where higher scores indicate a greater ability to discriminate between targets and distractors.

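### The confirmatory CB-Abst versus CB-Mon contrast drops unverified visits in one randomised arm only, and no planned analysis is stated to restore the randomised comparison

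*SAP*

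**What the plan says.** The SAP (Participants) randomises regular cannabis users to CB-Abst or CB-Mon, 70 per arm. Its section on the key confirmatory effect defines the main test as follows: "The key confirmatory effect of interest for each outcome will be a dummy-coded contrast between CB-Mon (the referent, coded as 0) and CB-Abst". The effect is taken as an average across the post-baseline visits.

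Under Missing data, the SAP restricts what enters that contrast: "because we are interested in the effect of abstinence, only data with biochemically-verified abstinence will be included". It then specifies that "all data for the visit of and subsequent visits in which abstinence was no longer verified will be excluded for CB-Abst subjects". It also requires that "Subjects must have at least one post-baseline data point to be included in an analysis". A CB-Abst participant who is unverified by the first post-baseline cognitive visit therefore leaves the analysis altogether.

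CB-Mon has no corresponding rule. Protocol Section V lets CB-Mon participants stop using if they wish. Section III requires that cannabis users have no immediate plan to quit, which makes this less likely.

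The restriction matches the stated purpose. The SAP's first research question is whether cognition "improves for students abstinent from cannabis use for one month above and beyond any improvement observed for students engaging in continued use". Protocol Aim 3 and Section VI likewise define the cognitive comparison by quitting and not by assignment.

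**The concern.** Randomisation makes the two arms comparable as assigned. Removing visits after randomisation, in one arm, according to what participants did, gives up part of that protection. If staying verified is related to cognition beyond what the baseline score explains, the retained CB-Abst data come from a selected group and are compared with an unselected CB-Mon arm. The estimate could then show a benefit that abstinence did not cause, or hide or reverse a real one.

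The SAP describes its analyses as confirmatory. Without an as-randomised estimate beside the main one, a reader cannot judge how far the result depends on which CB-Abst participants stayed in.

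**Working it through.** **1. Does any planned analysis keep all randomised data?**

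| Analysis | Restores removed CB-Abst visits? |
|---|---|
| SAP secondary 1, group-by-time interaction | Not stated |
| SAP secondary 2, comparison with non-users | Not stated |
| SAP secondary 3: "We checked whether our conclusions were robust to the inclusion of covariates, examining the inclusion of age, CUDIT-R scores, and biological sex" | No; partial adjustment for selection |
| SAP secondary 4: "We reran the primary analysis using only observed values" | No; drops imputed values, keeps the removal |
| SAP Primary Outcomes, exploratory replication of the pilot's method | Population not described; smaller module set |
| Protocol Section VI, cognition | Groups defined by quitting |

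The SAP applies the same approach to its secondary outcomes.

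**2. The plan's own figures.** The Power section assumes 4% dropout per week. 0.96^4 = 0.849, which agrees with its stated retention of just under 85%. The 80% power cannot be reproduced because no variance components are given. The allowance covers dropout only, not lost verification.

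**3. Simulation inputs.**
- From the documents: 70 per arm; baseline plus four weekly scores; retest correlation 0.65 (the protocol gives 0.6 to 0.75); model adjusted for baseline and linear time, independence GEE with robust standard errors.
- Assumed, because the documents are silent: no true effect; weekly loss of verification h = 5%, 10% or 25%; correlation r between staying verified and mean post-baseline performance; no other dropout.

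Unverified by week 4 = 1 - (1 - h)^4 = 0.185, 0.344 and 0.684.

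**4. Bias in SD / rejection at two-sided 0.05 (%), normal outcome.** Imputed: 48 predictive-mean-matching draws pooled by Rubin's rule, with predictors as listed in the SAP (arm is not among them) and covariates assumed unrelated to outcome; 2000 replicates. Left out: 8000 replicates. Monte Carlo error is at most about 0.6 and 0.4 points.

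| h | Removed visits | r = -0.4 | r = 0 | r = 0.2 | r = 0.4 |
|---|---|---|---|---|---|
| 5% | imputed | -0.026 / 5.6 | 0.002 / 5.6 | 0.009 / 5.1 | 0.020 / 5.2 |
| 5% | left out | -0.032 / 6.8 | -0.001 / 5.4 | 0.013 / 5.6 | 0.033 / 6.5 |
| 10% | imputed | -0.046 / 7.2 | -0.001 / 4.6 | 0.020 / 5.7 | 0.046 / 7.2 |
| 10% | left out | -0.055 / 9.5 | -0.001 / 5.5 | 0.028 / 6.4 | 0.055 / 9.3 |
| 25% | imputed | -0.078 / 8.6 | 0.000 / 3.0 | 0.036 / 4.2 | 0.077 / 8.2 |
| 25% | left out | -0.106 / 17.2 | 0.001 / 5.8 | 0.051 / 8.2 | 0.109 / 18.3 |

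A 0-18 binomial outcome gave similar bias with visits left out (0.02 to 0.12 SD in absolute size). A separate simulation with the SAP's 4% weekly dropout, retest 0.68 and r = 0.4 defined against the baseline-adjusted level gave 0.034, 0.062 and 0.099 SD at 15%, 30% and 50% unverified by week 4.

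**5. The alphas that apply.** The SAP sets alpha by "dividing the desired error rate of 5% by the number of outcomes per module". Only one of the 17 listed primary outcomes (SST) is tested at 0.05. Rejection with visits left out, r = 0.4:

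| Alpha | h = 5% | h = 10% | h = 25% | Null rate (r = 0) |
|---|---|---|---|---|
| 0.025 | 3.4% | 5.2% | 12% | 2.4-3.2% |
| 0.0167 | 2.3% | 3.7% | 10% | 1.5-2.2% |
| 0.0125 | 1.9% | 3.1% | 8% | 1.3-1.8% |

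**6. What an as-randomised analysis would give.** With complete follow-up, bias is within 0.003 SD and rejection is 4.8-6.2%. If half of those who lapse miss all later visits, residual bias at r = 0.4 is about 0.01, 0.02 and 0.035 SD at 5%, 10% and 25% loss.

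Dilution, if benefit occurs only while abstinent, no CB-Mon visit is abstinent and nobody resumes abstinence: the mean of (1 - h)^k over k = 1 to 4 is 0.881, 0.774 and 0.513. With 10% of CB-Mon visits abstinent (assumed), subtracting 0.10 gives about 0.78, 0.67 and 0.41. Resumed abstinence would raise these shares.

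**The case against.** The strongest reply is that this is a declared estimand. The SAP asks about abstinence, gives its reason for the rule, and follows the protocol's comparison of quitters with continuing users. An as-randomised contrast answers a different question. That stands as a reason to keep the planned analysis. It does not remove the selection, and the baseline score, age, sex and CUDIT-R adjust only for what they measure.

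The second reply is that materiality is not shown. That is also fair: every bias figure rests on assumed loss rates and correlations, and bias is zero if loss is unrelated to cognition given baseline. The protocol's smallest detectable effect is 0.51 SD (for a different analysis). The largest left-out biases in the table are 0.033/0.51 = 6%, 0.055/0.51 = 11% and 0.109/0.51 = 21% of it.

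A reader might infer that the trial's false-positive rate is near 18%. The documents do not support this. That figure needs 25% weekly loss, a correlation of 0.4, removed visits left out, and an alpha that applies to one primary outcome in 17. A reader might also infer that an as-randomised analysis would be free of bias. That requires lapsed participants to keep attending. The protocol says that their voucher level is reset, not that they are withdrawn, but attendance is voluntary.

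**Conclusion.** The point holds as a gap in the supporting analyses. The confirmatory contrast is conditioned on staying verified in one randomised arm, and no listed analysis is stated to restore the comparison by assignment. The rule is openly stated and deliberate, so nothing here supports a reading that it was concealed or that the abstinence estimand is illegitimate.

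Size and direction are unknown, and the bias may be negligible. Under the assumptions above, there is no inflation at 5% weekly loss if removed visits are imputed, 6-7% rejection at 0.05 at 10% loss, and 4-9% at 25%, which is an extreme loss rate. The bias is larger if those visits are left out, and the SAP does not settle which applies. If they are imputed, the target becomes performance had participants stayed abstinent, under missing at random, and the listed predictors contain no post-baseline use or metabolite data.

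This should be fixed because the remedy is cheap, not because the planned result has been shown to be wrong.

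**What to change.** Keep the verified-abstinence contrast and state that it is conditioned on staying verified in one arm. Then:

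- Add the same model on all randomised cannabis users, by assigned arm, using all collected visits regardless of verification. Label it as added after the 02/03/2023 unblinding. Report estimates with confidence intervals, not new confirmatory tests.
- State whether removed visits are imputed.
- Report exclusions and missed visits by arm and visit, and the share of CB-Mon visits that were abstinent.
- Interpret the two estimates together: one targets abstinence, the other assignment.

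No new data are needed, so far as lapsed participants kept attending. Attendance is paid separately from abstinence, which favours this. The imputation must be rerun because the missing-data pattern changes: (17 primary + 2 secondary outcomes) x 48 imputations = 912 scripted model fits, plus one exclusion table.

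The downsides are that the analysis is post hoc, that its estimate is diluted as shown in the working, and that it removes the selection only to the extent that lapsed participants were still assessed.

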deviation of the outcome pooling over groups during the baseline visit. In other words, we normalized the contrast of interest by the baseline variation in the outcome.

Secondary analyses

We conducted the following secondary analyses:

1. We tested our assumption of an additive model by fitting a model that includes a group by time interaction (i.e., the product of the contrast between CB-Abst and CB-Mon and the linear time trend variable). We conducted an omnibus test comparing the simpler additive model to the more complex interaction model – if the associated Wald test is significant at $p < \alpha_M$ (i.e., the specified level of significance α for a given module M) this will indicate the presence of a group by time interaction. Post-hoc comparisons of the regression coefficients of the interaction model will also indicate, if abstinence was associated with improvements in cognitive performance, when such improvement occurred. This secondary analysis addresses the second research question of the study.
2. We examined how cognitive performance of the two groups of cannabis users (the contingency management and monitoring groups) also compares against the control sample of non-users. This secondary analysis addresses the third research question of the study. We therefore...
 - a. Analyzed data from all three groups.
 - b. Created two dummy-coded variables to represent the 3 levels (contingency management, monitoring, and non-users) for group status. We used the non-user group as the referent, and had separate variables for the CB-Abst and CB-Mon groups.
 - c. Assessed (1) an additive model (main effects for group and time), and (2) an interaction model (also including at the group x time interaction in addition to the main effects).

- d. Conducted an omnibus test comparing the simpler additive model to the more complex interaction model – if the associated Wald test is significant at $p < \alpha_M$ (i.e., the specified level of significance α for a given module M), this will indicate the presence of a group by time interaction.
- e. If a group by time interaction or a main effect of group was found, we ran post-hoc comparisons to examine (a) if the CB-Mon group had worse performance compared to the non-user group, (b) if the CB-Abst group did not differ compared to the non-user group or (c) if performance for the CB-Abst group improved to levels matching the non-user group.

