- Data were modeled using a normal distribution (i.e., the standard linear model).

1.2. The median of the response times for hits from the **RVP** module.

- The median over the set of response times for all correct responses (identification of target 3-digit sequences).
- Response time variable in milliseconds (ms), ranging from 100 to 1900 ms, with higher values indicating slower performance in detecting targets.
- Data were modeled using a normal distribution (i.e., the standard linear model).

Statistical model

We will use the same statistical models and approach for primary and secondary analyses as described for the primary outcomes. We will deem effects significant for $\alpha = 0.025$.

Power

Power was determined via an R script conducting a power analysis for a linear model with treatment and time effects, including a treatment by time interaction, and assuming subject-varying intercepts and slopes for change over time (Schoenfeld, 2009). The script can be found at the following link:

- <http://hedwig.mgh.harvard.edu/biostatistics/sites/default/files/public/powslopes.r>

We assumed each group would have an initial set of 70 subjects. Though we had a retention rate of 93% in our pilot trial with 100% of retained participants with complete data, power calculations assumed a conservative 4% drop-out per week (i.e., just under 85% retention at Week 4). Power was computed using outcomes from a prior study ([name] et al., 2018):

- The mean response latency (in ms) for correct responses from the Attention Switching Task (AST) module.
- The mean switching cost (in ms; equivalent to the multitasking cost in the MTT module) from the AST module.
- The mean response latency (in ms) to correct choice on a first attempt from the Delayed Match to Sample (DMS) module.

Though based on different modules from the CANTAB than those currently used, these outcomes were chosen because of (a) the availability of prior data, (b) compatibility with the assumptions of the power analysis software, and (c) because of their overlap with the domains of interest, as the AST (which is very similar to the MTT) examines executive functioning and the DMS examines memory.

Power analyses indicated we would have an 80% chance to detect a difference at 2-sided alpha of .05 if the true difference between CB-Abst and CB-Mon (assuming learning in both groups) over 4 weeks of abstinence was:

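### The imputation predictors in the SAP leave out randomised group, so imputed values carry only part of the CB-Abst versus CB-Mon difference

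*SAP*

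**What the plan says.** The SAP's Missing data section imputes missing outcomes 48 times by chained equations, using linear regression and predictive mean matching, and pools by Rubin's rule. The predictors are introduced by "Covariates for imputing missing values will be" and are three bullets: "Non-missing outcome values at other time points", the baseline outcome, and "The covariates listed above (age in years, biological sex at birth, baseline scores for CUDIT-R, and duration in years spent using cannabis". No part of the SAP says that imputation was run separately by arm.

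The same section requires at least one post-baseline value for inclusion and adds that "all data for the visit of and subsequent visits in which abstinence was no longer verified will be excluded for CB-Abst subjects". It does not say whether those excluded visits then count as missing and are imputed.

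The imputed data feed a contrast of CB-Abst with CB-Mon (Key confirmatory effect), "testing whether a constant effect of abstinence exists, averaged over all time points". Secondary analysis 1 tests the additive assumption by "fitting a model that includes a group by time interaction". Secondary analysis 4 checks the handling of missing data: "We reran the primary analysis using only observed values (we excluded values that were imputed".

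**The concern.** The imputation model is narrower than the analysis model in the one variable being tested. A missing CB-Abst value is drawn from a regression that does not know the participant's arm. Outcomes at other visits bring in part of the group difference indirectly, but not all of it, so imputed cells in the two arms lie closer together than they should.

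The back-reference in the third bullet does not bring group in. The Covariates section names the time trend, baseline outcome, age, sex and CUDIT-R.

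At stake is an understated benefit of abstinence in the primary contrast if the effect is constant or grows. A growing effect is understated more in the group-by-time test, which answers the SAP's second research question (when performance improves). The analyst-blind stage could not have shown the problem, because it used shuffled CB-Abst and CB-Mon labels and so had no real group difference to dilute.

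**Working it through.** **Inputs from the documents.** Weekly dropout: "power calculations assumed a conservative 4% drop-out per week" (SAP, Power). Pilot retention 93% and 70 participants per group (SAP, Power). Test-retest correlation 0.6 to 0.75 (protocol, Power Analysis). At least one post-baseline value (SAP, Missing data).

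**Assumed.** A mean effect of 0.40 SD over weeks 1 to 4: constant 0.40; growing 0.16, 0.32, 0.48, 0.64; waning the reverse. Loss is monotone and unrelated to outcome.

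**1. The SAP's retention figure.** 0.96^4 = 0.849, which agrees with the stated just under 85% at week 4.

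**2. Share of cells imputed.** Participants lost before week 1 are out of the analysis, so the missing shares at weeks 1 to 4 are 0, 1 − 0.96 = 0.040, 1 − 0.96² = 0.078 and 1 − 0.96³ = 0.115. The mean is 0.058.

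**3. Constant effect.** Without group as a predictor, imputed cells keep 0.46 to 0.58 of the difference in simulation. Loss = 0.058 × (1 − 0.58) to 0.058 × (1 − 0.46) = 0.024 to 0.031, a ratio of about 0.97. On 0.40 SD, 3% is 0.012 SD.

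**4. Growing effect.** The effect-weighted missing share is (0.32 × 0.040 + 0.48 × 0.078 + 0.64 × 0.115) / 1.60 = 0.078. Imputed cells keep 0.20 to 0.29. Loss = 0.078 × 0.71 to 0.078 × 0.80 = 0.055 to 0.062, a ratio of about 0.94.

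**5. Group-by-time slope, growing effect.** With week codes −3, −1, 1, 3, the full slope is (−3 × 0.16 − 0.32 + 0.48 + 3 × 0.64) / 20 = 0.080 per code unit. If imputed cells keep 0.25, the amounts lost at weeks 2 to 4 are 0.010, 0.028 and 0.055. The slope loss is (−0.010 + 0.028 + 3 × 0.055) / 20 = 0.009, or about 11%. Simulation gives 0.88 to 0.89.

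**6. Waning effect.** The effect-weighted missing share is (0.48 × 0.040 + 0.32 × 0.078 + 0.16 × 0.115) / 1.60 = 0.039. Imputed cells keep 0.91 to 1.17, so the ratio is 1.00.

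**7. Simulated ratios** (estimate divided by the full-data estimate from the same sample, group not in the imputation):

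| Loss | Constant | Growing | Waning |
|---|---|---|---|
| 1.8% per week, both arms (0.93^(1/4) = 0.982) | 0.985–0.99 | 0.97 | 1.00 |
| 4% per week, both arms (SAP) | 0.97 | 0.94 | 1.00 |
| 4% dropout, plus assumed 5% weekly loss of verified abstinence in CB-Abst, imputed | 0.95–0.97 | 0.90–0.92 | not run |
| The same, 10% | 0.93–0.96 | 0.86–0.88 | not run |
| Assumed total weekly CB-Abst loss of 15–25%, imputed | 0.94–0.88 | 0.86–0.75 | 1.00–1.02 |

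The last three rows rest on loss rates that the documents do not give. With group in the imputation model the ratio was 0.99 to 1.01 throughout. A 0–18 count outcome (assumed mean 9, SD 3) with predictive mean matching and a binomial fit gave the same ratios for the constant and growing effects. At 70 per arm with 48 predictive-mean-matching imputations and a 0.33 SD effect, attenuation at 4% dropout was 3.1% (constant) and 6.0% (growing) without group, against 0.7% and 0.4% with it. A steeper growth pattern, starting from zero at week 1, lost 7 to 8%.

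**8. Observed-only rerun.** At 4% dropout the ratios are 1.00 constant, 0.98 growing and 1.02 waning. At the assumed 15–25% CB-Abst loss they are 1.00, 0.95–0.89 and 1.05–1.10.

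**9. Power** (70 per arm, mean effect 0.30 SD, two-sided 0.05, correlation 0.65, 500 paired replicates, 8 imputations), without versus with group. At 4% dropout: 84.6% v 87.0% (constant) and 82.6% v 85.8% (growing). At the assumed 15% CB-Abst loss with those visits imputed: 75.6% v 79.6% and 67.6% v 82.8%. The Monte Carlo SE of each figure is about 2 points. The paired shift in the estimate at 4% is clear of noise: −0.009 (constant) and −0.018 (growing), each with SE 0.0005.

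**The case against.** The strongest reply is about size. The confirmatory effect is defined as constant over time, and for that the loss is about 0.012 SD at a dropout rate the SAP itself calls conservative. It is 1 to 1.5% at the pilot's retention, and the power difference of 2.4 points is close to simulation error. The growing-effect figure also assumes purely monotone loss. The SAP mentions modules skipped within a visit, and with 6% of cells missing intermittently the ratio is 0.979 to 0.983 for both constant and growing effects. The large figures need abstinence-loss rates that are not in the documents, and need excluded visits to be imputed, although leaving them out altogether is arguably the more natural reading. A rerun on observed data is already planned.

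The omission may also be one of wording only. The Covariates list leaves group out too, although group is plainly in that model. The imputation list still names years of use, which the Analyst-blind section says was dropped as a covariate, so the bullet may be unrevised text.

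Most of this stands as a limit on size. It does not remove the point. The rule as written gives a diluted estimate in the imputed analysis, which is the primary one. The rerun is secondary, covers only the primary analysis, and is itself off in the averaged contrast when the effect changes over time. The SAP's power calculation is for a treatment-by-time slope, so a growing effect is a case the plan itself has in view. Whether the code included group cannot be seen from the text.

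**Conclusion.** The concern holds and should be fixed. If the stated list was followed, a constant effect is understated by about 3% and a growing one by about 6% at 4% weekly dropout, with the group-by-time slope down by 11 to 12% in the growing case. These sizes assume monotone, outcome-independent dropout, visit correlations of 0.6 to 0.75 and growth no steeper than 1:2:3:4. Intermittent gaps bring the loss nearer 2%.

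If excluded CB-Abst visits are imputed, the loss grows with the rate of lost abstinence: roughly 3 to 5% (constant) and 8 to 10% (growing) at an assumed 5% per week on top of dropout, and up to 12% and 25% at an assumed total CB-Abst loss of 25% per week. The bias for a waning effect is near nil or slightly reversed. The cost is effect size and power, not false positives.

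**What to change.** Impute within each randomised group, or enter group as a predictor in each visit's imputation equation, which allows the group difference to vary by visit. Keep the 48 imputations and the pooling. State whether CB-Abst visits excluded as unverified are imputed or left out. Reconcile years of use with the Analyst-blind section, for instance by saying that it is kept only as an auxiliary imputation predictor.

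The SAP dates the unblinded analysis 02/03/2023, so this should be labelled a post-unblinding correction, with the existing and corrected results shown side by side. If the code already included group, correct the text and leave the analysis alone. The cost is one predictor, one rerun, two sentences in the SAP and a disclosed deviation. Adding group restores the estimate when loss does not depend on outcome; it does not by itself deal with relapse that is related to unobserved cognitive performance.
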